8.3 Abnormal Laboratory Findings

Where Screening safety laboratory tests (blood, urine) are found to be outside the reference range provided by the laboratory and the Investigator believes the results to be of clinical significance, the participant may be asked to return to the investigational site or have a nurse visit to allow for repeat sampling. If the abnormal finding has not reverted to normal or is regarded as being clinically significant, the participant will not be entered into the study but will be referred for further investigation, as appropriate. Throughout the study, abnormal or out of range values should be reviewed by the Investigator who should make a determination if the values are clinically significant.

8.4 Withdrawal Criteria

A participant's legally authorized representative is free to withdraw consent and discontinue participation in the study at any time, without prejudice to further treatment, according to standard clinical practice. A participant's participation in the study may also be discontinued at any time at the discretion of the Investigator.

If the study treatment or observations are discontinued in any participant, the reason will be recorded on the e-CRF and the Sponsor notified promptly.

8.5 Risks and Benefits

NNZ-2591 Oral Solution has been given to 28 healthy volunteers to date and was well tolerated. All reported AEs were mild or moderate and resolved during the trial. There were no SAEs. There were no clinically significant findings from safety laboratory tests, vital signs, or cardiac tests. The most common TEAEs deemed related to drug were a cluster of apparently related neurological symptoms that included somnolence/drowsiness, blurred vision/difficulty focusing, ataxia/unsteady gait, dizziness, and vertigo. The majority of these TEAEs occurred within 2 to 3 hours of initial dosing. All resolved spontaneously without requiring medical intervention. There were no clinically significant findings on the laboratory tests or ECGs and no laboratory renal or hepatic laboratory findings were observed.

Potential risks associated with the performance of the PTHS assessments include fatigue, frustration, and provocation of maladaptive behaviors related to frustration in the participants. Mild irritation or discomfort may be experienced from blood draws and ECG leads.

Participants may receive no direct benefit from participation in this study. However, participation will help the investigators better understand the safety of NNZ-2591 in people with PTHS. Information obtained from this study may help people with PTHS in the future. It might improve the way people with PTHS are treated and help them better manage their symptoms. Previous scientific information obtained from animal studies indicates that the signs and symptoms of PTHS might be reduced following administration of NNZ-2591. It is possible that participants will experience this same benefit following administration of NNZ-2591 IMP.

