5. INTRODUCTION

5.1 Pitt-Hopkins Syndrome

Pitt-Hopkins syndrome (PTHS) is a rare, neurodevelopmental disorder characterized by developmental delays, moderate to profound intellectual disability, absent/limited speech, distinctive facial dysmorphology, and breathing problems such as episodic hyperventilation and/or breath-holding while awake. Other common symptoms may include repetitive behaviors and social communication impairments, constipation, severe near-sightedness (myopia), sleep disturbances, and seizures.^{2,3}

Individuals with PTHS have distinct facial features that are important elements of the diagnostic criteria, including a square face with narrow forehead, thickened helix, wide nasal bridge, beaked nose characterized by down-turned nasal tip, flared nasal alae and wide nasal tip, full cheeks, wide mouth, full lips and a cupid bow upper lip.³⁻⁷ Myopia is observed in the majority of patients (48-88%) and strabismus and astigmatism are also observed.^{4,6-11}

Individuals with PTHS demonstrate severe developmental delay in motor milestones including delayed ambulation and delayed, or ultimately absent, speech. While moderate to profound intellectual disability has been reported across the literature, most individuals have severe to profound cognitive impairments. Mental age equivalents for development level that have been reported as between 3.5 to 36 months for individuals between 32 months and 32 years old. The majority of individuals (68%) have absent or limited speech (less than 5 words) and all have impaired speech. While between 46-70% of individuals are reported to be independently ambulatory, the majority of individuals have gait abnormalities including a wide-based ataxic gait, as well as impaired motor coordination and hypotonia. Adaptive function for individuals with PTHS is low with developmental equivalent scores of 20 or less.

Breathing abnormalities are a characteristic feature and affect 45%-86% of individuals with PTHS, in particular hyperventilation or hyperventilation with apnea (46%) when awake.^{3, 6-11, 15} GI problems are also highly prevalent, and can be severe, with around 35% needing corrective treatment.¹³ Chronic constipation, with an onset as early as infancy,^{8, 9} is particularly common (67%-85% of patients).^{6-11, 15}

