6.3.1.1 Primary Endpoints

Safety: Incidence of AEs and SAEs from commencement of IMP administration through to the time of the last study visit will be evaluated. Vital signs, laboratory measures, physical exam results (neurological, ophthalmologic, and general) urine output history, will also be evaluated from screening/baseline through the end of the study.

Tolerability: Tolerability will be assessed based on caregiver reports and the caregiver diary, required dosing adjustments or discontinuations, dosing compliance and AEs related to participant experience.

Pharmacokinetic:

NNZ-2591 PK concentrations will be listed by participant and time point for each dose level with actual time they were acquired. The concentrations will be summarized by time, dose level and age group. For the concentrations measured at trough points dose relationship will be examined statistically with age group and/or body weight of participant as covariate.

Overall exposure parameters for NNZ-2591 such as C_{max} and AUC_{tau} may be derived by sparse non-compartmental analysis (NCA). Additionally, PK concentrations of NNZ-2591 measured in pediatric

participants will be used to refine a population PK model developed from adult NNZ-2591 PK data and extrapolated to pediatric population. After refinement, complete profiles for each participant will be simulated using a range of variability of model parameters and individual covariate effects. A standard NCA approach will be used for simulated profiles to calculate parameters C_{max} , AUC_{tau} , etc. for characterization of NNZ-2591 exposure in pediatric participants.

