11.2 Safety Analyses

Safety analyses will be conducted on the Safety Population and based on the safety endpoints listed in Section 6.3.1. Adverse events and other safety data will be summarized as frequencies and percentages, described in terms of severity and potential attribution. Objective safety assessments will be summarized over time on study; shift tables at time points of interest may be generated. The safety analysis details will be specified in the Statistical Analysis Plan (SAP).

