### 7.4 Physical and Neurological Examination

The physical examination will be conducted at all in-clinic visits. The exam will note Normal and Abnormal readings. For each abnormal reading, clinical significance will be determined. The physical exam procedure will include the following organ systems: Head, ears, eyes, nose, and throat; Skin; Cardiovascular; Respiratory; Gastrointestinal; Genitourinary (as appropriate or indicated); Musculoskeletal; and Allergies. The exam will include an assessment for sign of bladder or kidney pathology including an exam of the abdomen and both flanks. Assessment of edema will also be done. Exam may include suprapubic exam (bladder palpation) if decreased urine output is noted.

A neurological examination will be conducted at all in-clinic visits. A standard neurological exam will be conducted to include an evaluation of mental status, cranial nerves, motor exam, sensory exam, cerebellar (coordination, gait), and reflexes.

A modified version of the physical and neurological exams will be done by a physician via telemedicine at the remote visits. As part of the in-home visit, the nurse will conduct a targeted physical exam including assessment of general appearance, an abdominal and a costovertebral angle tenderness exam, assessment for signs of cystitis, and an assessment of edema. Exam may include suprapubic exam (bladder palpation) if decreased urine output is noted.

All examination results will be reported as normal or abnormal. Clinical significance will be determined for abnormal results.

The results of all examinations will be presented in data listings.

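### The neurological exam, a primary safety measure, is only listed, and its normal/abnormal record is insensitive to worsening of gait, coordination and tone

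*Protocol*

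**What the plan says.** Protocol 8.5 describes the Phase 1 experience in healthy volunteers: "The most common TEAEs deemed related to drug were a cluster of apparently related neurological symptoms that included somnolence/drowsiness, blurred vision/difficulty focusing, ataxia/unsteady gait".

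Protocol 6.3.1.1 lists the exam among the primary safety endpoints: "Vital signs, laboratory measures, physical exam results (neurological, ophthalmologic, and general) urine output history, will also be evaluated". SAP 7 repeats this. Under the Schedule of Assessments the neurological exam is done at Visits 1, 3, 5, 7, 9, 11, 13, 16 and 17. Protocol 9.5.5 makes it a modified telemedicine exam at Visits 7, 11, 13 and 17. The in-clinic exam covers mental status, cranial nerves, motor, sensory and cerebellar function (coordination and gait), and reflexes.

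SAP 7.4 fixes the scale: "All examination results will be reported as normal or abnormal. Clinical significance will be determined for abnormal results". It also fixes the output: "The results of all examinations will be presented in data listings". The section plans no count, shift or change from baseline, and the SAP addendum does not alter it.

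Protocol 11.2 points the other way: "Objective safety assessments will be summarized over time on study; shift tables at time points of interest may be generated". SAP 2 says that the SAP governs where the two differ on planned analyses.

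On baseline status, Protocol 5.1 says that "the majority of individuals have gait abnormalities including a wide-based ataxic gait, as well as impaired motor coordination and hypotonia".

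**The concern.** The primary objective is safety and tolerability. The drug-related events that led in Phase 1 were neurological, with unsteady gait among them. The scheduled exam looks directly at coordination and gait, but a two-category result has little room to move in children who start in the abnormal category. With listings alone, a reader of the study report would have to compare visits child by child to find a pattern.

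The exam could serve as a systematic cross-check on adverse-event reporting in a single-arm, open-label study. As planned, it produces no summary that could do so.

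**Working it through.** **Step 1: the SAP's treatment of comparable safety measures.**

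| Measure | Result scale | Planned output |
|---|---|---|
| ECG interpretation (SAP 7.7) | normal / abnormal, with clinical significance | shift from baseline at each post-baseline visit, plus listings |
| Laboratory tests with normal ranges (SAP 7.3) | low / normal / high | change summaries and shift tables, plus listings |
| Vital signs (SAP 7.6) | numeric | summaries and change at each post-baseline visit, plus listings |
| Physical and neurological exam (SAP 7.4) | normal / abnormal, with clinical significance | listings only |
| Ophthalmic exam (SAP 7.5) | not stated | listings only |

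The ECG interpretation is scored in the same way as the neurological exam and gets a shift summary. The SAP gives no reason for the difference.

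**Step 2: what a normal-to-abnormal record can show.** Let b be the share of children abnormal on an item at baseline. If worsening is unrelated to baseline status, the share of true worsening that can appear as a normal-to-abnormal shift is 1 − b. The documents say only that the majority have these gait abnormalities, so every b below is an assumption.

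**Step 3: illustration with fixed counts.** Assume 20 children, of whom A are abnormal at baseline, and 6 who truly worsen. The expected number of visible shifts is 6(1 − b). The chance that none is visible is C(A,6) / C(20,6), with C(20,6) = 38,760.

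- b = 60%, A = 12: 2.4 expected; 924 / 38,760 = 0.024, about 2%.
- b = 80%, A = 16: 1.2 expected; 8,008 / 38,760 = 0.207, about 21%.
- b = 95%, A = 19: 0.3 expected; 27,132 / 38,760 = 0.70, or 70%.

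**Step 4: illustration across the planned sample size of 10 to 20.** Assume that each child worsens with probability q = 0.20. The chance of at least one normal-to-abnormal shift is 1 − (1 − q(1 − b))^N. The chance of at least one worsening on a record that captured change from baseline is 1 − (1 − q)^N.

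| N | b = 0.51 | b = 0.70 | b = 0.90 | b = 1.0 | change from baseline recorded |
|---|---|---|---|---|---|
| 20 | 0.87 | 0.71 | 0.33 | 0 | 0.99 |
| 10 | 0.64 | 0.46 | 0.18 | 0 | 0.89 |

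Both illustrations ignore changes in clinical significance among children already abnormal. They therefore understate what the existing data hold. The plan states no figure of its own on this point, so there is none to reproduce.

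**The case against.** The strongest reply is that worsening already reaches a tabulated primary safety endpoint. Protocol 10.6 requires a baseline sign that worsens after dosing to be recorded as an adverse event, and SAP 7.2 tabulates these events by preferred term, intensity, relatedness and dose level. The DSMC sees individual safety listings before each titration. This stands: worsening is not lost to the safety analysis. It does depend on judgement, because Protocol 10.5 limits abnormal assessments to those that the investigator finds clinically significant.

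A reader might infer three stronger things that the documents do not support.

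- **That worsening cannot appear in the exam at all.** The clinical-significance call can change, and children normal on an item at baseline can shift.
- **That alertness is mostly abnormal at baseline.** Protocol 5.1 documents gait, coordination and tone; intellectual disability is not reduced alertness.
- **That the exam is the only scheduled clinician measure of this signal.** The CGI-S and CGI-I have an ambulation domain, and the modified two-minute walk test is done at Visits 1, 3 and 16. These are efficacy measures, and in the walk test an assistant supports the child's balance, so they do not replace a safety summary.

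Four further limits stand.

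- Protocol 11.2 makes shift tables optional. Its commitment is to summaries over time, and one can argue whether a clinician's call counts as objective.
- Protocol 5.6 says that most Phase 1 events arose within 2 to 3 hours of the first dose. The Visit 3 exam precedes dosing and the next is at Week 2, so a shift table would not capture acute first-dose effects.
- With 10 to 20 children, listings can be read child by child.
- The CRF and the list of tables lie outside these documents, so free-text descriptions or an unlisted table may exist.

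**Conclusion.** The point holds as a gap in reporting combined with an insensitive scale. A named primary safety measure has no planned summary, although the protocol says that objective safety assessments will be summarised and the SAP does so for the similarly scored ECG interpretation. For gait, coordination and tone, a normal/abnormal record misses worsening in children already abnormal, unless the clinical-significance call changes.

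The size is illustrative only. The 2%, 21% and 70% rest on assumed baseline rates, 6 assumed worsenings among 20 children, worsening independent of baseline status, and one exam component. The conclusion does not depend on a particular value: the visible share falls as baseline abnormality rises, and reaches zero only if every child is abnormal. This is an inexpensive improvement to the safety report; adverse-event tabulation remains the main route of detection.

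**What to change.** **SAP 7.4.** Add a shift table from baseline (normally Visit 3 under SAP 5.2.4), by exam component where the CRF captures it, by visit and by dose level. Use three levels: normal; abnormal, not clinically significant; abnormal, clinically significant. Show the full in-clinic exams (Visits 5, 9 and 16) separately from the modified telemedicine exams (Visits 7, 11, 13 and 17), which are not like-for-like with Visit 3.

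**SAP 7.5.** Add the same Screening-to-EOT shift for the ophthalmic exam, as far as the recorded result categories allow.

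**Optional.** Add a field per component for worse, same or better than Visit 3. SAP 2.2 says that nobody was enrolled under protocol version 3.0, so this may help only participants still to be examined. The same open-label clinicians would complete it, so it adds sensitivity rather than independence.

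**Cost.** A few extra safety tables with small counts, and no new visit or procedure. SAP 7.4 says that the three neurological exam levels are already determined. Under SAP 5, tables defined before database lock count as a priori; later ones would be labelled post hoc.

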9. STUDY PROCEDURES

9.1 Overview of Study Visits

The Screening/Baseline period will be conducted over 4 to 6 weeks. The second visit during the Screening/Baseline period (Visit 2) should be conducted 2 weeks \pm 1 day after the Screening visit (Visit 1). The participant will then remain in Screening for an additional 2 to 4 weeks. The caregiver diary must be completed daily during the entire Screening/Baseline period whether it is 4 weeks or 6 weeks. The Screening visit (Visit 1) and Baseline visit (Visit 3) may be conducted over three consecutive days. It is preferrable that ECGs, safety labs and biomarker sample collection are conducted on the same day. No assessments can be conducted until informed consent has been given by the caregiver or legally authorized representative. Also, training for the caregivers on all caregiver completed assessments must be completed before the caregiver rater may complete the assessments. All assessments must be completed within the window for the visit, as shown in the Schedule of Assessments in Section 4. For Visit 3, all assessments must be completed before administration of the IMP.

The in-clinic visits will be conducted in person at the study site. As described below, safety and efficacy assessments will be completed by site personnel. The caregiver will also complete caregiver assessments the day of the visit or the day before the visit as described below (except the caregiver diary which is completed daily), and these will be reviewed by site personnel. In-clinic visits will be done at Screening (Visit 1), Baseline (Visit 3), Week 2 (Visit 5), Week 6 (Visit 9), and Week 13 (EOT, Visit 16). For all visits designated as in-clinic (Visits 1, 3, 5, 9 and 16), an in-person visit is preferred. Off-site assessments may be allowed due to extenuating circumstances due to the COVID-19 health emergency. All requests for off-site assessments must be approved in advance by the Sponsor or Medical Monitor.

The combined remote telemedicine/in-home visit will be done during Screening/Baseline at Visit 2, and post-enrollment at Week 1 (Visit 4), Week 4 (Visit 7), Week 8 (Visit 11), Week 10 (Visit 13) and Week 15 (Visit 17). The combined remote visit is conducted by the site via telemedicine or video facilities, and by a visiting nurse who will conduct assessments at the participant's home. These combination remote/in-home visits will be conducted simultaneously whenever possible, or they will ideally be conducted on the same day. If not possible, the telemedicine visit and the nurse visit may be conducted on separate days. In this case, the telemedicine portion and in-home nurse portion must be conducted over two consecutive days. During Screening (Visit 2), the Investigator will review the medical history to determine if there are any changes in symptoms from the Screening visit (Visit 1). At post-enrollment visits, the Investigator will do a review of AE/SAEs and tolerability and conduct a recent clinical history. A modified version of

the physical and neurological exam will be completed by the Investigator at the telemedicine visits based on the guidance documents provided to the Investigator. During the in-home component of the visit at Screening (Visit 2), the nurse will collect vital signs, weight, do a Targeted Physical Exam assessing general appearance, abdominal/costovertebral angel tenderness (CVA), and edema, and query oral intake. The nurse will review the caregiver diary during the visit and provide the caregiver with a new section of the diary. Post-enrollment, at the in-home component of the combined visit, the nurse will collect urine, vital signs, weight, and blood samples for a comprehensive metabolic panel (CMP), complete blood count (CBC) with differential, and coagulation (except Visit 1, when only CMP is collected). The nurse will conduct a Targeted Physical Exam assessing: general appearance; the abdomen and the CVA region for tenderness; the extremities and peri-orbital region for edema. A suprapubic exam (bladder palpation) to assess for urinary retention may be performed. The visiting nurse will also review the caregiver diary, provide the caregiver with a new diary section, query oral intake, and a review tolerability. At the post-treatment follow-up visit at Week 15, the visiting nurse will also collect a 12-lead ECG, in addition to the above assessments.

In-home only visits with a visiting nurse will be done at Weeks 3 (Visit 6), 5 (Visit 8), 7 (Visit 10), 9 (Visit 12), 11 (Visit 14), and 12 (Visit 15). At these visits, the nurse will collect urine, vital signs, weight, and a blood sample for the CMP. The nurse will also conduct a Targeted Physical Exam assessing general appearance, abdominal/CVA, and edema. A suprapubic exam (bladder palpation) to assess for urinary retention may be performed. The visiting nurse will review the caregiver diary, query oral intake, and review tolerability.

A combined remote visit or nurse-only in-home visit may be conducted in-clinic by the study staff if agreed upon by the Investigator and the caregiver. The site should inform the nursing service of such a change. If an unscheduled nurse visit is needed for follow-up (e.g. repeat labs or other assessments), this can be requested by the site with the nursing service. The site should inform the Medical Monitor if they require an unscheduled nursing visit or will conduct a remote visit in the clinic.

The nurse will send a report for all in-home nurse visits to the Investigator along with a copy of the completed Caregiver Diary. The Investigator is responsible for reviewing the Caregiver Diary and determining if any issues should be reported as an adverse event or require follow up. The visiting nurse will escalate any issues related to potential AE/SAEs, stopping criteria, major dosing issues or issues of potential safety concern to the Investigator the same day. Any changes noted will be provided to the Investigator who will be responsible for determining and reporting AE/SAEs.

9.2 Study Procedures by Visit

9.2.1 Visit 1 Screening/Baseline (in-clinic) – Week -4 (\pm 2 days)

The following assessments will be conducted and data collected during Visit 1:

- Eligibility
 - o Informed consent (mandatory)
 - O Consent for reuse of leftover Biomarker and PK samples (optional)
 - Inclusion/exclusion criteria
 - Medical history
 - Confirm documented PTHS diagnosis and genotype
 - o PTHS history and exam
 - Confirm co-morbid psychiatric disorders by Diagnostic and Statistical Manual of Mental Disorders, Fifth Edition (DSM-5)
 - o Autism Mental Status Exam

- Rapid SARS-CoV-2 Test
- Safety
 - Physical and neurological examination 0
 - 0
 - 0
 - Vital signs
 - Height/length
 - Weight 0
 - o 12-lead ECG
 - CBC with differential 0
 - Coagulation
 - o CMP
 - Urinalysis (including screen for drugs of abuse)
 - TSH, Free T3, Free T4
 - HbA1c 0
 - Serum pregnancy test (females who have reached menarche only)
- Review the instructions for the Caregiver Diary and completing the clinical section for seizure types and breathing events
- Biomarkers
 - Blood sample for biomarkers
 - Stool sample for microbiome analysis
- Efficacy
 - o CGI-S
 - o SB5 or Bayley-4 (Bayley-4 is done for participants who cannot attain basal on the SB5)
 - Caregiver Top 3 Concerns
 - o ABC-2
 - CSHQ
 - 0 GIHQ
 - Modified two-minute walk test

The screening visit (Visit 1) may be conducted over three consecutive days. Eligibility assessments as outlined above should be done on the first day of the visit. It is preferrable that ECGs, safety labs and biomarker sample collection are conducted on the same day. No assessments can be conducted until after informed consent has been given by the participant's legally authorized representative. Also, training for the caregivers on all caregiver-completed assessments must be completed before the caregiver rater may complete the assessments. All assessments including caregiver completed assessments must be completed within the window for the visit (visit day ± 2 days).

9.2.2 Visit 2 Screening/Baseline (telemedicine and in-home) – 2 Weeks from Visit 1 $(\pm 1 day)$

The Screening/Baseline period will be conducted over 4 to 6 weeks. The second visit during the Screening period (Visit 2) should be conducted 2 weeks ± 1 day after the Screening visit (Visit 1).

Visit 2 of the Screening/Baseline period will be a remote telemedicine and in-home visit. The assessments to be conducted and data collected are divided accordingly below.

Remote/Telemedicine - Investigator and Appropriate Staff

The following assessments will be conducted and data collected during Visit 2, conducted by the site via telemedicine or video facilities as appropriate. Caregiver assessments must be completed the day of the visit or no earlier than the day before the visit (except the caregiver diary which is completed daily) and reviewed by the Investigator.

- Medical history (any updates since Visit 1)
- Review of the Caregiver Diary (con-meds, seizures, voids, oral intake, breathing events, changes in symptoms)

Caregiver Assessments

The following assessments should be completed by the caregiver. Caregiver assessments must be completed the day of the visit or no earlier than the day before the visit.

- Efficacy
 - o Caregiver Top 3 Concerns
 - o ABC-2
 - o CSHQ
 - o GIHQ

In-home Nurse Visit

The following assessments should be conducted, and data collected by the visiting nurse in the participant's home during Visit 2:

- Vital Signs
- Targeted Physical Exam: abdominal, CVA tenderness, general appearance, edema. Exam may include suprapubic exam (bladder palpation) to assess for urinary retention if decreased urine output is noted.
- Weight
- Review of Caregiver Diary

